mobile technologies. Our work is unique because we go beyond simply sending tips or reminders. Rather, our interventions prescribe tailored behavior change goals, prompt tracking of these goals via mobile technologies and then send immediate tailored feedback. As a result, we have been successful in achieving high rates of tracking adherence^{17,20} I aim to leverage my experience working on digital health intervention trials to improve adherence to the DASH diet among women with hypertension.

This study will have several areas of impact. We will establish the feasibility of a novel digital health-based approach for disseminating the DASH diet for women, using Nutritionix, a commercially available diet tracking app that thousands of Americans are already using. The data from this pilot feasibility trial will set the foundation for a larger, fully-powered R01 grant to examine whether DASH Cloud can improve blood pressure outcomes among women with hypertension. This proposal will focus on the following specific aims.

Aim 1: To modify existing technology platforms and develop content for the DASH Cloud intervention for women with hypertension or pre-hypertension.

Aim 2: To test the feasibility of the DASH Cloud intervention compared to education control among women with hypertension or pre-hypertension (n=up to 65) via a 3-month randomized controlled trial.

- Utilization of intervention components – daily diet tracking rates, and clicks to skills training materials.
- Change in dietary patterns – 3-month change in DASH diet adherence score (as measured from 24-hour recalls)
- Acceptability - patient satisfaction and intention for continued use as measured by surveys.

Aim 3: To evaluate the preliminary efficacy of the DASH Cloud intervention relative to education control on blood pressure, weight, and medication adherence at 3 months.

Design and Procedures

Study Design

We will enroll up to 200 adult women aged 21-70 with pre-hypertension or hypertension in order to qualify up to 65 to be randomized in a 3-month randomized controlled trial to test the initial feasibility of *DASH Cloud*, a digital health intervention for women with HTN. More details are described below.

Selection of Subjects

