Setting: We will recruit community participants from the Durham, NC area. Using designated space at the Sarah W. Stedman Center for Nutrition and Metabolism at Duke and Duke Digital Health, participants will complete baseline and follow-up visits where they will complete physiological and survey-based data collection.

Sample: We will randomize participants to either the DASH Cloud intervention or to DASH Light_education control and follow up at 3 months.

Inclusion/Exclusion:

Inclusion: ages 21-70 years; BMI >18.5 kg/m²; on self-reported use antihypertensive medication or self-reported systolic blood pressure 120-159 mmHg and/or diastolic blood pressure of 80-99; current use of a smartphone with an updated operating system, data plan, willingness to be texted daily or weekly; an active email account; spoken and written English fluency.

Exclusion: CVD event in prior 6 months; active malignancy; active psychosis or recent psychiatric institutionalization; current pregnancy or lactation; current participation in a similar trial.

Subject Recruitment and Compensation

We will recruit participants using a multi-pronged strategy: 1) we will distribute flyers at local gyms, community centers, grocery stores, and health and wellness stores; 2) we will collaborate with Duke Early Phase Clinical Research (formerly DCRU) and the Duke Primary Care Research Consortium (PCRC) to request that they query their database for subjects who fit the inclusion/exclusion criteria and email them information about the study, including a link to the study websites (dashcloud.org or dashcloudstudy.com). These URLs do not contain study information, rather they just redirect participants to the REDCap screening survey; 3) we will use social media (Twitter and Facebook) to advertise the study and direct interested subjects to the study web site, and; 4) we will email community organizations, including local health departments and churches, information about the study, including a link to the study web site. 5) We will use the contact list for participants who were ineligible for Study D0822 Comparing Self-Monitoring Strategies for Weight Loss (Campus IRB) that acknowledged they were interested in being contacted for other studies. 6) We will use ResearchMatch.org to connect with potentially eligible subjects. We have used these methods successfully in many of our team's previous studies.

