Those who respond to study marketing will undergo preliminary eligibility screening via a REDCap eligibility survey linked from our study website. Those who are deemed potentially eligible will be given a link to a video outlining study participation (<https://www.youtube.com/watch?v=4UW23zTuaZQ>). Interested participant will then be asked to complete an online consent form. After the consent form is signed, participants will be sent a REDCap link to fill out questionnaires asking about sociodemographic and behavioral characteristics.

Participants will be asked to complete 2 dietary recalls on the ASA-24 website. Study staff will send instructions to the participant to download and setup the Nutritionix app before their initial baseline visit. If needed, participants will be provided assistance from study staff to download and setup the app at the initial baseline visit. They will then be asked to take part in an initial baseline study visit at the Sarah W. Stedman Center for Nutrition and Metabolism at Duke or Duke Digital Health. At the first visit, the study staff will complete physiological data collection to confirm final eligibility. Participants with a blood pressure outside the upper range of eligibility will be told they can no longer participate. At this visit, study staff will provide instructions for how to use the app. We will ask women to track their diet for one week. After one week, if they successfully tracked at least 4 of 7 days, they will be asked to attend a 2nd baseline visit where they will be randomized and enrolled in the study. At this visit, participants will also receive a 30-minute in-person, individual orientation to the DASH diet to learn what is required in each study group. Participants who do not qualify based on non-inclusion, exclusion, or non-consent will be tabulated, noting the reason for non-participation. All subjects who attend the two baseline visits will receive a Duke ClinCard with a value of \$25. Enrolled subjects will receive another \$25 via their ClinCard after attending the 3-month follow up visit.

Consent Process

INFORMED CONSENT

The informed consent process for this study involves several components.

- First, participants will hear about the study from one of the previously-described recruitment methods.

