- 1) Diet tracking: proportion of participants completing daily dietary self-monitoring
- 2) Review of skills training: number of clicks to skills training via video tracking software.

DASH adherence: Dietary intake data will be collected using NCI's Automated Self-Administered 24-hour Recall tool (<https://asa24.nci.nih.gov/>). Participants will be prompted via email by study staff to complete the ASA-24. We will collect 2 dietary recalls at baseline and 3 months. To determine DASH adherence, we will use a previously determined index based on 11 food groups (e.g., fruits) and nutrients (e.g., sodium). We have experience using the ASA-24 in a previous trial with much success.

Patient satisfaction: We will use measures that we have delivered successfully in prior studies.

Blood pressure: Blood pressure will be measured at baseline and 3 months in the upper arm in triplicate at 1-minute intervals. Measurements will be obtained by trained study staff using the validated Omron HEM-907XL blood pressure monitor.

Sociodemographics: We will collect self-reported age, race/ethnicity, health insurance, income, employment status, education, current health status, household size, and marital status at baseline only.

Risk/Benefit Analysis

The primary risk to the subject is loss of confidentiality. The mobile technology carries a higher risk of this than the other stored data due to the nature of mobile technology and the servers used to deliver the intervention. We will follow data security plans used in our previous and current studies, which were developed with the guidance of Duke Office of Information Security. The details are explained below in the data and safety monitoring section.

Potential benefits for study participants include improved blood pressure and consequent reduction in cardiovascular risk. An additional benefit for some participants may be personal satisfaction in being part of a study that may have major public health implications for the community. No benefit from participation can be guaranteed. Potential benefits to others include the possibility that this research will help researchers evaluate the feasibility and efficacy of the DASH Cloud system in promoting DASH diet adherence. The minimal health risks to participants listed above are offset by the potential benefits to them and to society.

Cost to the Subject

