IRB Pro00081972
Version 11/06/17

Data Analyses and Statistical Considerations

We will perform descriptive analyses to determine engagement and feasibility. Linear mixed modeling will be used to test for across group differences in DASH adherence and other secondary outcomes. Our model will include group, time, and a group by time interaction, and will be fitted with a full maximum likelihood method using all data. As this is a feasibility study, we have estimated sample size from our previous text messaging trial where we saw strong engagement; 50% texted daily and 85% texted at least 2 days/week.

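### A repeat blood pressure triplicate at the existing second baseline visit, averaged with the first, would modestly tighten the Aim 3 estimate at little cost

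*Protocol*

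**What the plan says.** Protocol, Subject Recruitment and Compensation: "At the first visit, the study staff will complete physiological data collection to confirm final eligibility". The next sentence shows that blood pressure is part of this: "Participants with a blood pressure outside the upper range of eligibility will be told they can no longer participate". A week of diet tracking follows, and then: "After one week, if they successfully tracked at least 4 of 7 days, they will be asked to attend a 2nd baseline visit". Randomisation and an individual diet orientation are listed for that second visit. Blood pressure is not.

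Protocol, Measures, Blood pressure: "Blood pressure will be measured at baseline and 3 months in the upper arm in triplicate at 1-minute intervals". It does not say which of the two baseline visits is meant.

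Aim 3 of the protocol reads: "To evaluate the preliminary efficacy of the DASH Cloud intervention relative to education control on blood pressure, weight, and medication adherence at 3 months". The number randomised is given under Study Design: "in order to qualify up to 65 to be randomized in a 3-month randomized controlled trial".

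The SAP (and the matching protocol section) specifies a linear mixed model with group, time and their interaction, fitted by full maximum likelihood, with no baseline covariate. The sample size rests on engagement: "we have estimated sample size from our previous text messaging trial where we saw strong engagement; 50% texted daily". No SD, correlation, power or precision target is given for blood pressure.

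**The concern.** Blood pressure varies within a visit and also from one visit to another. Three readings a minute apart deal with the first source and leave the second untouched. In the planned model the group-by-time term is, with complete data and two time points, the difference between arms in mean change. A change score carries the visit-level noise of the baseline in full, on top of that of the 3-month visit.

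With at most 65 women, the Aim 3 contrast will be imprecise whatever is done. A second pre-randomisation occasion would remove part of the noise, and the visit at which it could be taken already exists. Aim 3 also feeds a later, fully powered trial on blood pressure. Two occasions before any intervention would give a direct estimate of visit-to-visit variation, a planning quantity that the documents do not contain.

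**Working it through.** **The plan's own figure.** There is none to reproduce. The limit of 65 is not derived from any blood pressure quantity.

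**Inputs**
- From the documents: up to 65 randomised; one scheduled baseline occasion (triplicate); one 3-month occasion; model without a baseline covariate.
- Assumed: between-woman systolic SD 10-14 mmHg; visit-to-visit SD 6-10 mmHg; correlation r of true pressure over 3 months 0.8-1.0, with true pressure taken as unchanged over the run-in week; 32 women per arm; complete data.

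**Formulas.** Let B be the between-woman variance, W the visit-to-visit variance, and c = r × B. The variance per woman is:
- planned model, one baseline visit: 2(B + W) − 2c
- planned model, mean of two visits: (B + W) + (B + W/2) − 2c
- baseline-adjusted, one visit: (B + W) − c²/(B + W)
- baseline-adjusted, mean of two: (B + W) − c²/(B + W/2)

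The standard error of the contrast is √(2 × variance / 32).

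**Middle case** (SDs 12 and 8, r = 0.9): B = 144, W = 64, c = 129.6, c² = 16,796.

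| Analysis | Baseline | Variance | SE (mmHg) |
|---|---|---|---|
| Planned model | visit 1 | 416 − 259.2 = 156.8 | 3.13 |
| Planned model | mean of two | 208 + 176 − 259.2 = 124.8 | 2.79 |
| Baseline-adjusted | visit 1 | 208 − 16,796/208 = 127.2 | 2.82 |
| Baseline-adjusted | mean of two | 208 − 16,796/176 = 112.6 | 2.65 |

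- Repeat visit under the planned model: 124.8/156.8 = 0.796, so 20% less variance and 11% less SE.
- Adjustment alone: 127.2/156.8 = 0.81, so 19% less variance and 10% less SE.
- Repeat visit on top of adjustment: 112.6/127.2 = 0.885, so 11.5% less variance and 6% less SE.

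**Range over the assumed inputs**
- Planned model. The cut in variance is (W/2) / [2W + 2B(1 − r)]. It is largest at r = 1, where it is 25% (SE down 13%). It is smallest at SDs 14 and 6 with r = 0.8: 18/150.4 = 12% (SE down 6%).
- Baseline-adjusted. It is smallest at SDs 10 and 10 with r = 0.8: 168.0 to 157.3, or 6% (SE down 3%). It is largest at SDs 14 and 6 with r = 1: 66.4 to 52.5, or 21% (SE down 11%).

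**Second parameterisation.** This uses a total SD of 12, arms of 32 and 33, and a correlation of 0.6 between any two visits. The planned model gives SE 2.66 with one baseline visit and 2.31 with two (95% half-width 5.2 to 4.5 mmHg). With adjustment the figures are 2.38 and 2.21 (half-width 4.7 to 4.3). If the two baseline visits correlate more strongly with each other than with month 3, by 0.1-0.2, the SE falls by about 6-11% under the planned model and 3-5.5% with adjustment. The direction was the same in every setting tried.

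**Upper cut-off.** Visit-1 systolic pressure was truncated at 160 in simulation, with mean 130-140 and SD 12-15. This removed about 1-9% of women and moved mean change by about 0.1-1.3 mmHg in both arms alike. The SE ratios barely changed.

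**The case against.** **The baseline visit is not defined.** The protocol calls both visits baseline visits, and its Setting paragraph speaks of baseline visits in the plural as the place for physiological data. A visit-2 measurement is unlisted, not ruled out. This stands: visit 1 as the Aim 3 baseline is a fair inference and no more.

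**A reader might infer that baseline rests on one reading.** It does not. It is one occasion with three readings, and only the variation between visits is left to reduce.

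**A reader might infer that the eligibility cut-off biases Aim 3.** The same measurement does remove women at the top, so within-arm change carries some regression to the mean. But the cut-off is applied before randomisation and affects both arms alike, and Aim 3 is a comparison with control. The cut-off is no reason for the repeat, which would in any case keep the truncated visit-1 value in the average.

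**Baseline adjustment gets most of the gain without a new measurement.** This stands in the middle case (SE 2.82 against 2.79). The two measures add, but the second step is smaller, about 6% in SE.

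**Blood pressure is a preliminary outcome.** The trial is sized on engagement, and its primary feasibility outcome is use of the intervention components. The 5.5 mmHg effect in the Background comes from a feeding trial and is not a planning effect here. This also stands, and it limits the weight of the point.

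**Conclusion.** The point holds as an inexpensive improvement worth considering. The only baseline blood pressure occasion that the documents schedule is the visit-1 triplicate. A second occasion at visit 2 would reduce the SE of the Aim 3 contrast by about 6-13% under the planned model, or 3-11% with baseline adjustment. In the middle case that is 0.34 mmHg (3.13 to 2.79) or 0.17 mmHg (2.82 to 2.65). These figures rest wholly on assumed SDs and correlations and on complete data in 32 women per arm; fewer women would raise every SE but leave the ratios unchanged.

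A reader might infer that the gain is large or that the present plan is faulty. The documents support neither. The gain is modest, the contrast is unbiased as planned, no stated precision target is missed, and nothing in the text is contradictory. What is missing is a statement of which visit defines baseline.

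**What to change.** 1. In Measures, Blood pressure, and in the SAP, state which visit or visits supply the baseline value for Aim 3.
2. Consider repeating the triplicate at visit 2 with the same device, before allocation is revealed and before the diet orientation, and define baseline as the mean of the two visits. Eligibility would continue to rest on the visit-1 measurement, as now written.
3. Consider a baseline-adjusted or baseline-constrained model in the SAP. It needs no new data and in the middle case gives about the same gain as the repeat; together they bring the SE from 3.13 to 2.65 mmHg.

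The cost is a few minutes at a visit that already takes place, with the same staff and monitor, and a sentence or two in each document. The downside is a slightly longer second visit.

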IRB Pro00081972
Version 11/06/17

Data Analyses and Statistical Considerations

We will perform descriptive analyses to determine engagement and feasibility. Linear mixed modeling will be used to test for across group differences in DASH adherence and other secondary outcomes. Our model will include group, time, and a group by time interaction, and will be fitted with a full maximum likelihood method using all data. As this is a feasibility study, we have estimated sample size from our previous text messaging trial where we saw strong engagement; 50% texted daily and 85% texted at least 2 days/week.

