Protocol Full Title: DASH Cloud: Using digital health to improve adherence to the DASH diet among women at risk for cardiovascular disease

Short Title: DASH Cloud

Purpose of the Study

One-third of women have hypertension (HTN), and the risk of cardiovascular disease (CVD) because of HTN is more serious among women than men. Until recently, however, efforts to reduce CVD mortality focused primarily on men. The DASH diet is a proven behavioral strategy to reduce blood pressure, however, national adherence rates are poor. Using digital health tools may help to improve adoption of the DASH diet.

Digital health approaches capitalize on the ubiquitous utilization of mobile technologies and have broad dissemination potential. There have been few efforts to test a DASH intervention via digital health and none directed to women. This proposal will leverage a commercial diet tracking application and our existing intervention technology platform to test the feasibility of DASH Cloud, a digital health intervention for women with pre-hypertension and hypertension. The primary outcome is DASH diet adherence.

Background and Significance

Women need better interventions for hypertension self-management. One-third of and pre and postmenopausal women have hypertension¹ and only half of those women have their blood pressure under control. Uncontrolled blood pressure is the strongest predictors of heart disease – the leading cause of death among women. This is because heart disease is more serious among women than men. After a heart attack, women have lower survival rates and a poorer quality of life. Despite these gender-based differences in outcomes, our understanding is limited about how to address the unique issues that women face in managing hypertension behaviorally. Developing behavioral interventions specifically for women in the pre- and postmenopausal period is critical to alleviating the burden of hypertension and heart disease among women.

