No costs are incurred by the subject, unless the subject is charged for receiving text messages or data usage for watching videos. This is very uncommon, and if it occurs, the cost is typically less than 3 cents per text received.

Data Analyses and Statistical Considerations

We will perform descriptive analyses to determine engagement and feasibility. Linear mixed modeling will be used to test for across group differences in DASH adherence and other secondary outcomes. Our model will

include group, time, and a group by time interaction, and will be fitted with a full maximum likelihood method using all data. As this is a feasibility study, we have estimated sample size from our previous text messaging trial where we saw strong engagement; 50% texted daily and 85% texted at least 2 days/week.

Data and Safety Monitoring

Study records that identify patients will be kept confidential as required by law. All data will be marked with a unique code number for storage at Duke University Health System in accordance with Duke's Institutional Review Board's guidelines and policies. All data collection will occur in private settings where patient survey responses cannot be seen or heard by others. Patients can refuse to answer any of the questions or stop participation in this study at any time.

Mobile technology: Information collected by Nutritionix mobile app is subject to the terms of use. Many apps make claims that they are secure, compliant with federal privacy regulations, and used and tested by other academic centers. However, any mobile app that is downloaded carries potential security risks, and Duke cannot guarantee that these mobile apps are free of risk. Some apps may be able to perform hidden functions or may have security flaws that allow unauthorized access to information. We are unable to fully tell participants what information these mobile apps can access or change on their phone or what information from their phone may be stored outside of Duke. Participants will be encouraged to limit personal identifiers entered into mobile applications only to those that they wish to voluntarily share with others.

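### The planned mixed model gives each arm its own baseline mean; a shared baseline mean, or adjustment for baseline, would usually estimate the same 3-month effect more precisely at almost no cost

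*SAP*

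**What the plan says.** The SAP (Data Analyses and Statistical Considerations) plans a linear mixed model for DASH adherence and the other outcomes: "Our model will include group, time, and a group by time interaction". The protocol section of the same name says the model will "include group, time, and a group by time interaction, and will be fitted with a full maximum likelihood method using all data". No baseline covariate and no constraint on the baseline means is stated for any outcome.

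The Measures section gives two time points. For diet: "We will collect 2 dietary recalls at baseline and 3 months". For blood pressure: "Blood pressure will be measured at baseline and 3 months in the upper arm in triplicate at 1-minute intervals".

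Subject Recruitment and Compensation sets the order of events. The diet recalls are listed before the first baseline visit. Physiological data are collected at that visit. After a week of tracking, women who qualify move to the next step: "they will be asked to attend a 2nd baseline visit where they will be randomized and enrolled in the study". The same section caps entry blood pressure: "Participants with a blood pressure outside the upper range of eligibility will be told they can no longer participate".

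Purpose of the Study states: "The primary outcome is DASH diet adherence". Aim 2 names the 3-month change in the DASH score as the quantity of interest.

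**The concern.** A group main effect together with group-by-time gives each arm its own baseline mean. The baseline measures are scheduled before allocation, so the two expected baseline means are equal by design, and the model spends information estimating a difference known to be zero. With complete data the group-by-time coefficient is simply the difference in mean change. That estimate subtracts the whole of any chance baseline imbalance, although only part of a baseline difference carries forward to 3 months.

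At stake is the width of the confidence interval for the between-arm comparison of DASH score in at most 65 women, and likewise for blood pressure and weight. Bias is not at issue, because both analyses are unbiased under randomisation. The target is also the same: when the arms share one baseline mean, the between-group difference at 3 months is the between-group difference in 3-month change.

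**Working it through.** **Inputs from the documents.** Up to 65 women randomised (Study Design), two time points (Measures), and the model terms and full maximum likelihood fit (SAP).

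**Assumptions.** Allocation is 32 v 33, since no ratio is stated. Every woman has a baseline value. Ten women are missing at 3 months (10/65, about 15%), leaving 27 v 28. The correlation rho runs from 0.3 to 0.95. The ratio k = 3-month SD / baseline SD is 1, 1.25 or 1.5.

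**The plan's own figure.** The sample size is attributed to engagement rates in an earlier trial. No alpha, power, effect size, SD, correlation or dropout is given, so there is no precision figure to reproduce.

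**Step 1: complete data, equal SDs.** Variance of the effect:
- planned model: SD² × 2(1 − rho) × (1/n1 + 1/n2)
- shared baseline or ANCOVA: SD² × (1 − rho²) × (1/n1 + 1/n2)

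The ratio is (1 + rho)/2, so the saving is (1 − rho)/2: 35%, 25% and 15% at rho 0.3, 0.5 and 0.7. Estimating the slope inflates the adjusted variance by about 1 + 1/(65 − 4) = 1.016. The ratios become 0.66, 0.76 and 0.86, that is, savings of 34%, 24% and 14%, and simulation gave the same.

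**Step 2: dropout under full maximum likelihood.** The planned fit also uses women with a baseline only, so it is no longer exactly the completers' difference in change. With all baselines present,

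planned estimate = A − (1 − b) × D,

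where A is the completers' ANCOVA estimate (also the common-baseline maximum likelihood estimate), b the pooled slope and D the baseline mean difference among all randomised women. A numerical fit to one simulated dataset (rho 0.5) confirmed this: planned 0.4628 by both routes; common-baseline 0.3952, equal to ANCOVA 0.3952; completers' change 0.3976. Across simulated trials the planned estimate usually lies close to the completers' change: at rho 0.5 the typical gap is 0.05 against a standard error of 0.27.

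The large-sample saving is

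(1 − rho·k)² C_N / [(1 − rho·k)² C_N + k²(1 − rho²) C_n],

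with C_N = 1/32 + 1/33 = 0.0616 and C_n = 1/27 + 1/28 = 0.0728. At rho 0.5 and k = 1: 0.25 × 0.0616 = 0.0154; 0.75 × 0.0728 = 0.0546; 0.0154 / 0.0700 = 22%.

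| rho (k = 1) | Formula | Simulated saving | Equivalent extra women |
|---|---|---|---|
| 0.3 | 31% | 30% | about 42% |
| 0.5 | 22% | 20% | about 26% |
| 0.7 | 13% | 11% | about 13% |
| 0.9 | 4% | 2% | about 2% |
| 0.95 | 2% | 0% | none |

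The simulation used 40,000 trials per cell with values missing at random. The last column is 1/(1 − saving) − 1, taken from unrounded savings where they differ.

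**Step 3: power, as illustration only.** For an assumed true effect of 0.6 SD at the two-sided 5% level, power rises from 48% to 62%, 60% to 70% and 81% to 86% at rho 0.3, 0.5 and 0.7 (60,000 trials per rho).

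**Step 4: unequal SDs, same dropout.**

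| k | rho 0.3 | rho 0.5 | rho 0.7 |
|---|---|---|---|
| 1.25 | 17% | 8% | about 0 |
| 1.5 | 10% | 2% | −1% |

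This may apply to blood pressure, which is capped at entry but not at 3 months. If the baseline SD is instead the larger, at 1.25 times the 3-month SD, the complete-data variance ratio is 0.50 to 0.64 over rho 0.3 to 0.8, a saving of 36% to 50%.

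**The case against.** The strongest reply is that nothing here is wrong. Group, time and group-by-time under full maximum likelihood is a standard, unbiased model that keeps all the data, and its interaction maps directly onto Aim 2. The trial is a feasibility study with no power claim, and the fully powered test is left to a later grant. The status of the DASH score is also mixed. Purpose of the Study calls it the primary outcome, but the Measures section names use of the intervention components as the primary feasibility outcome, and the wording of the analysis paragraph can be read as placing DASH among the secondary outcomes. The power figures rest on an effect size, correlation and dropout rate that the documents do not give.

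Most of this stands as a limit on how much the point matters, and the power figures are illustrative. It does not remove the case for the change: the SAP does plan to test between-arm differences with this model, Aim 3 seeks preliminary efficacy, and precision is scarce at 65 women.

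Two technical objections also deserve weight. The change is not strictly free: one slope is estimated, and the worst case simulated was about 1% more variance. And the condition stated for reaching randomisation is tracking on at least 4 of 7 days, not completed recalls, so some women may lack a baseline DASH score. ANCOVA would then drop women whom the plan keeps; the common-baseline mixed model would not, and is the better choice for that reason. A recall completed after allocation would not satisfy the shared-mean assumption, so the timing should be checked.

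**Conclusion.** The concern holds. The planned model is valid but usually less precise than a shared-baseline or baseline-adjusted analysis of the same data. With equal SDs and about 15% missing at 3 months, the variance saving is about 30%, 20% and 11% at rho 0.3, 0.5 and 0.7, falling to about 2% at 0.9 and nil at 0.95. Weight may lie at that upper end, and blood pressure may gain less if its 3-month SD is the larger. The case is strongest for the DASH score: with only two recalls per time point a moderate correlation is plausible, though this too is an assumption. The change should be made because the likely gain is useful and the downside negligible, not because the planned result would mislead.

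**What to change.** In the analysis paragraph of both the SAP and the protocol, replace the model sentence. Specify a mixed model with time and group-by-time but no group main effect, so that both arms share one baseline mean, with an unstructured 2×2 covariance and all randomised women included. Name the between-group difference at 3 months from this model as the test for the DASH score, and use the same model for blood pressure and weight. Regressing the 3-month value on group and baseline is an acceptable alternative and gives the same estimate when every woman has a baseline.

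The cost is one sentence in each document. No new data or participants are needed, and the statistical price is the one estimated slope.
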